
 
To describe COVID-19 related healthcare resource utilization in nonhospitalized symptomatic participants <math>\geq 12</math> years of age with COVID-19 who are immunocompromised and treated with nirmatrelvir/ritonavir.
 
	
 
Proportion of participants with COVID-19-related hospitalization of any duration.
 
Proportion of participants with COVID-19-related ICU admission of any duration.
 
Proportion of participants requiring invasive mechanical ventilation or ECMO.
 
Number of days in hospital and ICU stay in participants with COVID-19-related hospitalization.
 
	
 
Not applicable.
 

Objectives	Endpoints	Estimands
	
 
Number of COVID-19-related medical visits through Day 44 and through Week 24.
 
	

 
To evaluate nirmatrelvir/ritonavir for the duration and severity of signs and symptoms in nonhospitalized symptomatic participants <math>\geq 12</math> years of age with COVID-19 who are immunocompromised.
 
	
 
Duration of each targeted COVID-19 signs/symptoms.
 
Proportion of participants with severe signs/symptoms attributed to COVID-19 through Day 44.
 
	
 
Not applicable.
 

 
To determine the PK of nirmatrelvir/ritonavir in nonhospitalized symptomatic participants <math>\geq 12</math> years of age with COVID-19 who are immunocompromised.
 
	
 
Nirmatrelvir and ritonavir PK in plasma and whole blood (if feasible).
 
	
 
Not applicable.
 

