### 9.3.3. Secondary Endpoint(s)/Estimand(s) Analysis

Details on the definitions and analyses of secondary endpoints will be described in the SAP. Secondary endpoints include:

- Time to first NP swab SARS-CoV-2 RNA <LLOQ (<2.0 log10 copies/mL) for participants with NP swab SARS-CoV-2 RNA  $\geq$ LLOQ at baseline.
- Time to sustained NP swab SARS-CoV-2 RNA <LLOQ (<2.0 log10 copies/mL) through Day 44 for participants with NP swab SARS-CoV-2 RNA  $\geq$ LLOQ at baseline.

- Proportion of participants with SARS-CoV-2 RNA <LLOQ in plasma over time.
- Proportion of participants with SARS-CoV-2 RNA level in NP swabs <2.0 log10 copies/mL at each study visit through Day 44.
- Change from baseline in SARS-CoV-2 RNA level in NP swabs and in plasma over time.
- Rebound in SARS-CoV-2 RNA level in NP swabs at follow up (ie, any study visit after end of treatment through Day 44) that is defined as a half (0.5) log10 copies/mL increase or greater in SARS-CoV-2 RNA level relative to end of treatment SARS-CoV-2 RNA level based on treatment regimen, with a follow-up viral RNA level ≥2.5 log10 copies/mL.
- Incidence of TEAEs.
- Incidence of SAEs and AEs leading to discontinuations.
- Proportion of participants with COVID-19-related hospitalization >24 hours, or death from any cause through Day 28.
- Proportion of participants with death (all cause) through Week 24.
- Proportion of participants with COVID-19-related hospitalization of any duration.
- Proportion of participants with COVID-19-related ICU admission of any duration.
- Proportion of participants requiring invasive mechanical ventilation or ECMO.
- Number of days in hospital and ICU stay in participants with COVID-19-related hospitalization.
- Number of COVID-19-related medical visits through Day 44 and through Week 24.
- Duration of each targeted COVID-19 signs/symptoms.
- Proportion of participants with severe signs/symptoms attributed to COVID-19 through Day 44.
- Nirmatrelvir and ritonavir PK in plasma and whole blood (if feasible).

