6.2.8. Incidence of SAEs and AEs leading to discontinuations

The incidence of SAEs and AEs leading to discontinuation will be summarized by treatment group using the safety analysis set.

6.2.9. Proportion of participants with COVID-19-related hospitalization >24 hours, or death from any cause through Day 28

The proportion of participants with COVID-19-related hospitalization >24 hours, or death from any cause through Day 28 will be summarized. The cumulative proportion of participants hospitalized for the treatment of COVID-19 or death during the first 28 days of the study will be estimated for each treatment group using the Kaplan-Meier method to take account of losses to follow-up and summarized graphically for each treatment group.

For participants without an event who complete the Day 28 assessment, they will be censored at Day 28. For participants without an event who discontinue or are lost to follow-up before the Day 28 assessment, they will be censored at the last known date in the study.

6.2.10. Proportion of participants with death (all cause) through Week 24

The proportion of participants who died from any cause through Week 24 will be analyzed using the method specified in Section 6.2.9 and summarized for each treatment group. KM plots for each treatment group will also be provided. Participants without an event will be censored at the last known date in the study.

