6.2.11. Proportion of participants with COVID-19-related hospitalization of any duration

The proportion of participants with COVID-19-related hospitalization of any duration will be analyzed using the method specified in Section 6.2.9 and summarized by treatment arm

DMB02-GSOP-RF02 7.0 Statistical Analysis Plan Template 31-Jan-2022 PFIZER CONFIDENTIAL TMF Doc ID: 98.03 Page 20 of 32 through day 44 and through week 24. Participants without an event (at Day 44/Week 24) will be censored at that time or at the last known date in the study, whichever is later.

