6.2.13. Proportion of participants requiring invasive mechanical ventilation or ECMO

The proportion of participants requiring invasive mechanical ventilation or ECMO will be analyzed using the method specified in Section 6.2.9 and summarized by treatment arm through day 44 and through week 24. Participants without an event (at Day 44/Week 24) will be censored at that time or at the last known date in the study, whichever is later.

6.2.14. Number of days in hospital and ICU stay in participants with COVID-19-related hospitalization

The number of days of hospital stay and number of days of ICU stay in participants with COVID-19-related hospitalization will be summarized through Day 44 and through Week 24 by treatment group using descriptive statistics (ie, mean, median, range).

6.2.15. Number of COVID-19-related medical visits through Day 44 and through Week 24

The number of COVID-19-related medical visits through Day 44 and through Week 24 will be summarized by treatment group using descriptive statistics (ie, mean, median, range).

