Rebound in SARS- CoV-2 RNA up to Day 28 (NP) defined as a half \log_{10} copies/mL increase or greater relative to EOT (active) with follow-up viral RNA level \geq 3.0 \log_{10} copies/mL	Secondary	Evaluable with EOT (active) and 1 post-EOT not missing	No imputation for missing data	Descriptive (n, %)
Proportion with COVID-19-related hospitalization >24 hours, or death through Day 28	Secondary	Evaluable	Max censor time at Day 28	KM method
Proportion with death (all cause) through Week 24	Secondary	FAS	Max censor time at Week 24	KM method
Proportion with COVID-19-related hospitalization	Secondary	Evaluable	Max censor time at Day 44	KM method
Proportion with COVID-19-related ICU admission	Secondary	Evaluable	Max censor time at Day 44	KM method
Proportion requiring IMV or ECMO	Secondary	Evaluable	Max censor time at Day 44	KM method
Number of days in hospital and ICU stay	Secondary	Evaluable, participants with COVID- 19-related hospitalizat ion	In the absence of a specific record of a COVID-19-related hospitalization, participants will be considered to be out of hospital	Descriptive summary

DMB02-GSOP-RF02 7.0 Statistical Analysis Plan Template 31-Jan-2022 PFIZER CONFIDENTIAL TMF Doc ID: 98.03 Page 28 of 32

Endpoint	Analysis Type	Population	Data Inclusion and Rules for Handling Intercurrent Events and Missing Data	Analysis Model
Number of COVID- 19-related medical visits through Day 44 and through Week 24	Secondary	Evaluable	In the absence of a specific record of a COVID-19-related medical visit, participants will be considered to not have a COVID- 19-related medical visit.	Descriptive summary
Duration of each targeted COVID-19 signs/symptoms	Secondary	Evaluable	No imputation for missing data	KM method
Proportion with severe signs/symptoms attributed to COVID-19	Secondary	Evaluable	No imputation for missing data	Descriptive (n, %)

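### Hospital and ICU days are summarised by arm only among participants who were hospitalized, so the arm means are not a randomized comparison of resource use and can move opposite to it

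*SAP*

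**What the plan says.** Protocol Section 3 sets an objective of describing "COVID-19 related healthcare resource utilization in nonhospitalized symptomatic participants" who are immunocompromised and receive the study drug. One of the five endpoints under it, listed again in Protocol 9.3.3, is "Number of days in hospital and ICU stay in participants with COVID-19-related hospitalization".

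SAP 6.2.14 carries this forward. Hospital days and the "number of days of ICU stay in participants with COVID-19-related hospitalization will be summarized" for each arm at two horizons, Day 44 and Week 24, as mean, median and range. The Appendix 1 row for this endpoint limits the population to Evaluable participants who had a COVID-19-related hospitalization. Its data rule reads: "In the absence of a specific record of a COVID-19-related hospitalization, participants will be considered to be out of hospital".

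The neighbouring endpoint under the same objective, the number of COVID-19-related medical visits (SAP 6.2.15), is handled differently. Appendix 1 takes it over the whole Evaluable set and treats the absence of a visit record as no visit.

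**The concern.** The objective concerns resource use in the treated participants, but the days table covers only those who were admitted. Admission is an outcome that treatment duration may change. The admitted participants in the 5-, 10- and 15-day arms may therefore be different kinds of patient, and randomization no longer protects a comparison of their means.

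If a longer course prevents mainly the short admissions, the remaining stays are the long ones. The arm's mean then rises while its total use falls, and a reader who takes the row as resource use by duration gets the wrong direction. The out-of-hospital rule in Appendix 1 would naturally give zeros to participants never admitted, but the restricted population removes them. No planned table gives days per participant or total bed-days directly.

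**Working it through.** The documents give no expected rate or length of stay for this endpoint, so there is no planned figure to reproduce. The stay lengths below are assumed and only show the mechanism.

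**Inputs.** About 50 participants per arm in the main study population (SAP 2.4). Conditional mean = total days / number hospitalized. Per-participant mean = total days / 50.

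**Illustration 1: short stays prevented.**
- 5-day arm, stays 3, 3, 9, 9: total 24. Conditional mean 24/4 = 6.0. Per participant 24/50 = 0.48.
- 15-day arm, stays 9, 9: total 18. Conditional mean 18/2 = 9.0. Per participant 18/50 = 0.36.
- Conditional ratio 9.0/6.0 = 1.50, that is 50% more. Actual-use ratio 18/24 = 0.75, that is 25% less.

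**Illustration 2: other assumed stays.**
- Arm A, five stays of 2 days and five of 12: total 70. Conditional mean 70/10 = 7.0. Per participant 70/50 = 1.4.
- Arm B, the five short stays prevented: total 60. Conditional mean 60/5 = 12.0. Per participant 60/50 = 1.2.
- The direction reverses again.

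**Illustration 3: long stays prevented.** Start from the 5-day arm of illustration 1 and remove the two 9-day stays, leaving 3 and 3: total 6. Conditional mean 6/2 = 3.0. Per participant 6/50 = 0.12. Both figures fall, so reversal depends on which admissions are prevented.

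**How many participants the table rests on (assumed range).** Expected number hospitalized per arm = 50p. Chance that at least one of three arms has none = 1 - (1 - (1 - p)^50)^3.

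| p | Source | Expected per arm | At least one arm empty |
|---|---|---|---|
| 0.77% | 8/1039, treated high-risk adults, Protocol 2.2.1 | 0.4 | 97% |
| 5% | assumed | 2.5 | 21% |
| 10% | assumed | 5.0 | 1.5% |

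The 0.77% comes from a different population followed to Day 28. This endpoint covers immunocompromised participants to Day 44 and Week 24, so the table shows a range and predicts nothing.

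**The case against.** The strongest reply is that the endpoint is what its name says. The protocol defines it among the hospitalized, the SAP repeats that condition, and length of stay is a legitimate question. It is one of 18 secondary endpoints in Protocol 9.3.3. SAP 5.1 rules out hypothesis testing, and only mean, median and range by arm are planned. Frequency is covered elsewhere: "The proportion of participants with COVID-19-related hospitalization of any duration will be analyzed using the method specified in Section 6.2.9", and ICU admission and ventilation or ECMO are treated likewise (SAP 6.2.12 and 6.2.13). Medical visits, which Protocol 8.2.2 defines to include hospitalizations, are counted over the whole Evaluable set. Total bed-days also follow from number times mean: 4 × 6.0 = 24 and 2 × 9.0 = 18. A careful reader who has the number hospitalized can see the reversal.

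All of this stands, and it limits the weight of the point. It does not make the arm means a comparison of use, and it leaves the reader to reconstruct the figure that matches the objective.

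Three stronger readings are tempting, and the documents do not support them.

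- *A longer course will look worse.* Illustration 3 shows that it need not.
- *Early death in hospital is wrongly counted as low use.* For a resource-use objective, a participant who dies on the second hospital day did use two bed-days. Neither SAP 6.2.14 nor Appendix 1 says how days after death count, because the Appendix 1 rule concerns absent hospitalization records. Mortality has its own endpoint in SAP 6.2.10: "The proportion of participants who died from any cause through Week 24 will be analyzed". Days alive and out of hospital would be a new clinical endpoint and is a matter of preference.
- *The small numbers are caused by the restriction.* They come from rare events. With one or two admissions in an arm, days per participant would rest on the same one or two people.

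**Conclusion.** The point holds as a cheap improvement. The planned by-arm summary of hospital and ICU days conditions on a post-randomization outcome, so it describes length of stay and is not a randomized comparison of resource use. It can move opposite to actual use: 6.0 against 9.0 days conditionally, while use is 0.48 against 0.36 days per participant. That size rests wholly on assumed stays. The possibility of reversal is arithmetic, but whether it would occur in this trial is unknown. The sparsity figures are an assumed range and do not carry the conclusion. No tested result depends on this endpoint, and the companion proportions already show part of the picture.

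**What to change.** In SAP 6.2.14 and the matching Appendix 1 row, add hospital days and ICU days per participant over the whole Evaluable Analysis Set, through Day 44 and through Week 24. Count 0 for participants with no COVID-19-related hospitalization record, as SAP 6.2.15 and Appendix 1 already do for medical visits. Show the mean and the total bed-days by arm, since the median will usually be 0. State in a footnote that, as for visits, time without a record counts as no use, including after loss to follow-up.

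Keep the protocol-defined hospitalized-only summary as a description of length of stay, with the number hospitalized and the number of deaths per arm beside it. Days alive and out of hospital is optional.

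The cost is SAP wording and one extra table. Admission and discharge dates and ICU status are already collected (Protocol 8.2.2), and the Schedule of Activities records medical visits through Week 24. Protocol Section 9 lets the SAP modify the outlined analyses and ties an amendment only to major changes in the primary endpoint. The downside is a distribution that is mostly zeros, and the addition does not make rare events less rare.

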6.2.16. Duration of each targeted COVID-19 signs/symptoms

Duration of each targeted COVID -19 signs/symptoms is defined as (First Date when the symptom alleviated/resolved) – (First Dose Date) +1 for each participant with baseline severity of mild, moderate, or severe.

For a participant that either completes the Day 44 visit of the study or discontinues from the study before the Day 44 visit without alleviation/resolution of signs/symptoms (censored), censoring date will be at the date of discontinuation from the study or day 44 whichever comes first, and time will be calculated as (Censoring Date) – (First Dose Date) +1.

Symptoms Alleviation through day 44 of each targeted COVID-19 sign/symptom is defined as **the first time** when each targeted symptom scored as moderate or severe at study entry are scored as mild or absent AND a targeted symptom scored mild or absent at study entry are scored as absent.

Symptoms Resolution through day 44 of each targeted COVID-19 sign/symptom is defined as the first time when each targeted symptom scored as mild, moderate or severe at study entry are scored as absent.

DMB02-GSOP-RF02 7.0 Statistical Analysis Plan Template 31-Jan-2022 PFIZER CONFIDENTIAL TMF Doc ID: 98.03 Page 21 of 32 For symptoms with no reported severity in baseline, the symptom will have to be absent in order to be counted as alleviated/resolved (missing severity at baseline will be treated as mild).

For duration of each targeted COVID19 sign/symptom, a Kaplan-Meier analysis providing the event rate, median and quartiles will be provided for each treatment arm.

6.2.17. Proportion of participants with severe signs/symptoms attributed to COVID-19 through Day 44

Participants will record a daily severity rating of their symptom severity over the past 24 hours based on a 4-point scale in which 0 is reported if no symptoms were present; 1 if mild; 2 if moderate; and 3 if severe.

Vomiting and diarrhea will each be rated on a 4-point frequency scale where 0 is reported for no occurrence, 1 for 1 to 2 times, 2 for 3 to 4 times, and 3 for 5 or greater. Sense of smell and sense of taste will each be rated on a 3-point Likert scale where 0 is reported if the sense of smell/taste was the same as usual, 1 if the sense of smell/taste was less than usual, and 2 for no sense of smell/taste.

The proportion of participants with any severe targeted signs/symptoms attributed to COVID-19 through Day 44 will be summarized by treatment group. A participant with severe score for any targeted symptoms post-baseline will be counted as severe. Additionally, the proportion of participants reporting the presence of each targeted sign and symptom that is mild, moderate, or severe categories over time will also be presented.

In addition, to understand the severity of signs/symptoms attributed to COVID-19, the following analysis will be performed:

- 1. Proportion of participants with any severe targeted signs/symptoms attributed to COVID-19 at DAY 1 (baseline).
- 2. Proportion of participants with any severe targeted signs/symptoms attributed to COVID-19 Day 2 to end of active study treatment (during treatment; treatment arm dependent).
- 3. Proportion of participants with any severe targeted signs/symptoms attributed to COVID-19 from end of active treatment to Day 44 (post treatment).

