## **8.2. Efficacy Assessments**

### **8.2.1. Participant Diary**

Participants will be provided an electronic handheld device or will use their own device to record study intervention administration (as well as reason for changed or missed dose), signs and symptoms of COVID-19, and PRO assessments in the study diary.

Participants will receive daily reminders to complete entries on their own as specified in the [SoA](#). The diary should be completed at approximately the same time every day. Staff will review the participant's study diary online as specified in the [SoA](#).

The diary allows recording of these assessments only within a fixed time window (next calendar day), thus providing an accurate representation of the participant's experience at that time. The participant is able to make revisions to incorrect entries before pressing the save or submit button. In the event that a participant becomes aware of an error in data after the entry is saved, a change to the diary data may only be made by the investigator submitting a data clarification form. Data reported in the participant diary will be transferred electronically to a third-party vendor, where they will be available for review by investigators and the sponsor or delegate at all times via an internet-based portal.

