6.2.1.1. Main Analysis

Time (days) to first NP swab SARS-CoV-2 RNA<LLOQ (<2.0 log₁₀ copies/mL) will be evaluated for participants with NP swab SARS-CoV-2 RNA \geq LLOQ at baseline. The first day of NP swab SARS-CoV-2 RNA<LLOQ will be considered the First Event Date. Time

DMB02-GSOP-RF02 7.0 Statistical Analysis Plan Template 31-Jan-2022 PFIZER CONFIDENTIAL TMF Doc ID: 98.03 Page 17 of 32 (days) to first NP swab SARS-CoV-2 RNA<LLOQ will be calculated as (First Event Date) – (First Dose Date) +1.

There are limitations to the timing of the first event date as NP viral RNA is generally only captured at in-person scheduled visits during the study.

The Day 44 visit day is the last possible day the NP swab SARS-CoV-2 RNA<LLOQ can be achieved.

For a participant that either completes the Day 44 visit of the study or discontinues from the study before the Day 44 visit without NP swab SARS-CoV-2 RNA<LLOQ (censored), censoring date will be at the last date on which NP swab SARS-CoV-2 RNA is assessed, and time will be calculated as (Censoring Date) – (First Dose Date) +1 or the Day 44 visit whichever occurs first.

Time to NP swab SARS-CoV-2 RNA<LLOQ will be summarized graphically using Kaplan-Meier plots for each of the treatment groups in main study population.

6.2.2. Time to sustained NP swab SARS-CoV-2 RNA <LLOQ (<2.0 log10 copies/mL) through Day 44 for participants with NP swab SARS-CoV-2 RNA ≥LLOQ at baseline

Time (days) to sustained NP swab SARS-CoV-2 RNA<LLOQ (<2.0 log₁₀ copies/mL) will be evaluated. Sustained is defined as NP swab SARS-CoV-2 RNA level not \geq 2.0 log₁₀ copies/mL at any study visit (through Day 44) following the first study visit where the participant's NP swab SARS-CoV-2 RNA <LLOQ.

Let *t* represent the number of days between 5 and 35 inclusive for which there is a protocol-specified measurement of SARS-CoV-2 RNA level on Day *t*.

Then a sustained event will correspond to the first possible value of *t* to satisfy the following criteria:

- a) The Day 44 SARS-CoV-2 RNA level is <LLOQ
- b) The Day t SARS-CoV-2 RNA level is <LLOQ
- c) All available (non-missing) protocol-specified SARS-CoV-2 RNA measurements between Day *t* and Day 44 are <LLOQ
- d) No more than one of the protocol-specified SARS-CoV-2 RNA measurements between Day *t* and Day 44 are missing.

There are limitations to the timing of the first event date as NP viral RNA is generally only captured at in-person scheduled visits during the study.

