The Day 35 visit is the last possible day the sustained NP swab SARS-CoV-2 RNA<LLOQ can be achieved.

DMB02-GSOP-RF02 7.0 Statistical Analysis Plan Template 31-Jan-2022 PFIZER CONFIDENTIAL TMF Doc ID: 98.03 Page 18 of 32 The time to the sustained event is defined as:

- For a participant with sustained event at Day *t*, the First Event Date is the date of the Day *t* measurement, and time to event will be calculated as (First Event Date) (First Dose Date) +1.
- For a participant for which no possible value of *t* ≤ the 35 visit satisfies the criteria for a sustained event (censored), censoring date will be the date of the last available protocol-specified SARS-CoV-2 RNA measurement other than Day 44, and time will be calculated as (Censoring Date) (First Dose Date) +1.

Time to sustained NP swab SARS-CoV-2 RNA<LLOQ will be summarized graphically using Kaplan-Meier plots for each of the treatment groups in main study population.

6.2.3. Proportion of participants with SARS-CoV-2 RNA <LLOQ in plasma over time.

• The proportion of participants with SARS-CoV-2 RNA <LLOQ as measured in plasma will be summarized at each study visit through week 24 for each treatment arm. In addition, 95% CIs for the proportion of participants with SARS-CoV-2 RNA <LLOQ in plasma at each study visit will be calculated for each treatment arm.

6.2.4. Proportion of participants with SARS-CoV-2 RNA level in NP swabs <2.0 log₁₀ copies/mL at each study visit

The proportion of participants with SARS-CoV-2 RNA < 2.0 log₁₀ copies/mL as measured by NP swab will be summarized at each study visit through Week 24 for each treatment arm. In addition, 95% CIs for the proportion of participants with SARS-CoV-2 RNA <2.0 log₁₀ copies/mL as measured by NP swabs at each study visit will be calculated for each treatment arm.

6.2.5. Change from baseline in SARSCoV-2 RNA level in NP swabs and in plasma over time.

Descriptive statistics by treatment group for the change from baseline to each study visit (Day 5, 10, 15, 21, 28, 35, 44) will be provided. Participants are excluded from the analysis for reasons of Not Detected, Zero or Missing baseline and/or post-baseline viral load results.

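### Symptom duration is censored at study discontinuation or Day 44, not at the last rating, so a participant who stops rating an unresolved symptom but stays in the study is carried event-free through unrated time

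*SAP*

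**What the plan says.** SAP 6.2.16 measures duration from first dose to the first recorded alleviation or resolution of each targeted symptom. Without such a record, the "censoring date will be at the date of discontinuation from the study or day 44 whichever comes first". For each symptom, "a Kaplan-Meier analysis providing the event rate, median and quartiles will be provided for each treatment arm".

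The two viral endpoints follow another convention. In SAP 6.2.1.1 the "censoring date will be at the last date on which NP swab SARS-CoV-2 RNA is assessed". In SAP 6.2.2 the "censoring date will be the date of the last available protocol-specified SARS-CoV-2 RNA measurement other than Day 44".

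SAP Appendix 1 says that missing data are not imputed for symptom duration, and SAP 5.3 says the same of missing endpoint data generally.

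On data capture, SAP 6.2.17 says "Participants will record a daily severity rating of their symptom severity over the past 24 hours". Protocol 8.2.1 says "The diary allows recording of these assessments only within a fixed time window (next calendar day"), so a participant cannot fill in missed days afterwards. The protocol's Schedule of Activities lists signs and symptoms only at visits: Baseline, Days 5, 10, 15, 21, 28, 35 and 44, Weeks 12 and 24, and early termination.

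**The concern.** An event needs a recorded score. Once ratings stop, no event can occur, yet the 6.2.16 rule keeps the participant at risk until discontinuation or Day 44. Take someone with a cough on Day 12 who makes no further ratings but stays in the study. Days 13 to 44 enter the Kaplan-Meier estimate as observed time with the cough still present. That amounts to imputing persistence, although the SAP says that nothing is imputed.

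Stopping the diary is not the same as leaving the study. Protocol 7.1 keeps participants in follow-up after they stop study drug, and Protocol 7.3 treats a participant as lost only after repeated missed visits and failed contact.

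At stake are the event rate, median and quartiles that 6.2.16 reports by arm. The rule pushes the event rate down and the times up. If the share of in-study non-raters differed between arms, arms with the same recovery would show different curves.

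**Working it through.** **Plan's own figure.** The documents state no expected symptom duration and no diary-completion rate, so there is nothing to reproduce. What follows is a range under stated assumptions.

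**Who is affected under 6.2.16**

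| Participant | Under the SAP rule | Last-rating censoring |
|---|---|---|
| Improvement recorded before ratings stop | Event on that date | Same |
| Stops rating unresolved, discontinues that day | Censored that day | Same |
| Stops rating unresolved, discontinues later | Censored at discontinuation | Censored at last rating |
| Misses ratings but rates at Day 44 or early termination | Censored at about that date | About the same |
| Stops rating unresolved, stays in study | Event-free to Day 44 | Censored at last rating |

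Only the third and fifth rows carry unrated time. The fifth carries most.

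**Assumptions, none from the documents.** True resolution time is exponential with median m of 7, 10 or 14 days. A share f (10% to 40%) stops rating on a day uniform from 1 to 14, independently of recovery. Of those who stop, 0%, 50% or 100% discontinue the same day.

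**Hand calculation when nobody discontinues.** The chance of being unresolved on day s is 2^(−s/m). Let A be its average over s = 1 to 14.

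- Share carried event-free to Day 44: f × A.
- Loss in the Day 44 event rate: f × (A − 2^(−44/m)), because those who would still be unresolved at Day 44 are not lost events.

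Putting the numbers in:

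- m = 7, f = 0.10: A = 0.515; 2^(−44/7) = 0.013; loss = 0.10 × 0.502 = 5.0 points.
- m = 10, f = 0.20: A = 0.618; share carried = 12.4%; 2^(−4.4) = 0.047; loss = 0.20 × 0.571 = 11.4 points.
- m = 14, f = 0.40: A = 0.704; 2^(−44/14) = 0.113; loss = 0.40 × 0.590 = 23.6 points.

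In the middle case, if all of an arm of about 50 had the symptom at baseline, 0.124 × 50 ≈ 6 participants would be carried, fewer than the 10 who stop.

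**Simulation (200,000 participants, Kaplan-Meier), percentage resolved by Day 44**

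| m, f | Last-rating rule | SAP, none discontinue | SAP, half discontinue | SAP, all discontinue |
|---|---|---|---|---|
| 7 days, 10% | 98.8 | 93.7 | 96.1 | 98.8 |
| 10 days, 20% | 95.3 | 83.7 | 88.9 | 95.3 |
| 14 days, 40% | 88.8 | 65.2 | 74.2 | 88.8 |

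The losses are 5.1, 11.6 and 23.6 points with no discontinuation, which agrees with the hand calculation. They are 2.7, 6.4 and 14.6 points when half discontinue, and zero when all do.

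With nobody discontinuing, the median over the whole grid lengthens by 0 to 6 days (for example 11 to 12 days at m = 10, f = 20%; 15 to 21 at m = 14, f = 40%). The time to 75% resolved lengthens by 2 to 15 days (14 to 16 at m = 7, f = 10%; 20 to 35 at m = 10, f = 30%) or is not reached by Day 44. Simulated times are whole days and can differ by a day between runs.

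**Unequal stopping.** At m = 14, with 10% stopping in one arm, 30% in another, identical recovery and no discontinuation, the SAP rule gives 82.9% and 71.0% resolved by Day 44, a spurious gap of 11.9 points.

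**The case against.** A reader might infer that everyone who stops rating is counted as symptomatic to Day 44. The documents do not support that. The rule itself removes discontinuers on their discontinuation date, participants with recorded improvement are events, and Protocol 7.3 treats persistently unreachable participants as withdrawn.

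The schedule narrows the problem further. Both groups covered by the rule, Day 44 completers and early discontinuers, have a rating due at that last visit. Where it is done, the two rules nearly coincide, and intermittent gaps before it do not matter. The bias needs a participant who skips all later ratings, including the last one due, and yet is not withdrawn promptly. That is possible but is not the general case.

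The size rests on assumed inputs. A reader might also infer that the rule will distort the arm comparison. The documents give no reason to expect different diary adherence: the trial is double-blind and every arm takes study medication for 15 days. The 10% versus 30% contrast is an illustration only.

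No test or power is affected, and sampling error is large. Under an exponential with median 14 days, the standard error of the median with 50 participants is about 14 / (0.693 × √50) = 2.9 days. This limits the importance of a small shift in the median, but it does not remove the bias, which does not shrink with sample size and falls most on the Day 44 event rate and the time to 75% resolved.

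Finally, last-rating censoring is unbiased here only because stopping was made independent of recovery. If participants stop because they are worse, it is optimistic. If they stop because they feel well, the SAP rule is further from the truth. That caution stands.

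**Conclusion.** The point holds for a defined group: participants with an unresolved symptom who stop rating and remain in the study. SAP 6.2.16 carries them event-free through time without data, contrary to the SAP's own statement on imputation and to its convention for the swab endpoints.

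The direction is clear for that group, with event rates too low and times too long. The size is not known. Over the assumed range the Day 44 event rate falls by about 5 to 24 points if no stopper discontinues, by 2.7 to 14.6 points if half do, and by nothing if all do that day. Ratings still made at Day 44 or early termination reduce it further. The endpoint is secondary and descriptive, so the harm is to the reported curves and summaries and not to any formal conclusion.

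**What to change.** In SAP 6.2.16, for participants without recorded alleviation or resolution, censor each symptom at the date of its last non-missing rating on or before Day 44. Say that a participant with no post-baseline rating is censored at Day 1. Report, by arm and symptom, the number censored before Day 44. Also reconcile the daily rating in SAP 6.2.17 with the visit-based schedule in the protocol, because the schedule determines what counts as the last rating.

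The cost is a sentence or two of SAP text and a small change to the derivation. The downside is the assumption that stopping ratings is unrelated to recovery. Keeping the current rule as a sensitivity analysis covers this: if the two sets of curves agree, the choice does not matter, and if they differ, the counts of early censoring show where the difference arises.
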